### Tables

Table No.	Title	Population	Standard
Baseline and Demographic Characteristics			
1.1.1	Analysis Populations	All-Screened	X
1.1.2	Summary of Participant Disposition	FAS	X
1.1.3	Summary of Number of Participants Enrolled by Country and Site	FAS	X
1.1.4	Summary of Protocol Deviations	FAS	X
1.2.1	Summary of Demographics and Baseline Characteristics	FAS	X
1.3.1	Summary of Baseline Disease Characteristics	FAS	X
1.3.2	Summary of Prior Cancer Therapy	FAS	
1.3.3	Summary of Prior Systematic Cancer Therapy by WHO Drug Class and Preferred Term	FAS	
1.4.1	Summary of Prior Medications	FAS	X
1.4.2	Summary of Concomitant Medications	FAS	X
1.5.1	Summary of General Medical History	FAS	X
Efficacy			
2.1.1	Summary of Best Overall Response and Objective/Complete Response Rate as Determined by Independent Review Committee	FAS	
2.1.2	Summary of Best Overall Response and Objective/Complete Response Rate as Reported by Investigator	FAS	
2.1.3	Summary of Best Overall Response and Objective Response Rate as Determined by Independent Review Committee by Subgroup	FAS	
2.2.1	Summary of Duration of Response as Determined by Independent Review Committee	FAS	
2.2.2	Summary of Duration of Response as Reported by Investigator	FAS	
2.2.3	Summary of Progression-Free Survival as Determined by Independent Review Committee	FAS	
2.2.4	Summary of Progression-Free Survival as Reported by Investigator	FAS	
2.2.5	Summary of Overall Survival	FAS	
2.2.6	Summary of Best Change in Target Lesion Size as Determined by Independent Review Committee	FAS	
2.2.7	Summary of Best Change in Target Lesion Size as Reported by Investigator	FAS	
2.2.8	Summary of Best Change in Spleen Size as Determined by Independent Review Committee	FAS	
2.2.9	Summary of Best Change in Spleen Size as Reported by Investigator	FAS	

Table No.	Title	Population	Standard
2.4.1	Summary of Best Overall Response and Objective/Complete Response Rate as Determined by Independent Review Committee – Crossover as a Separate Treatment Group	FAS	
2.4.2	Summary of Best Overall Response and Objective/Complete Response Rate as Reported by Investigator – Crossover as a Separate Treatment Group	FAS	
2.4.3	Summary of Best Overall Response as Determined by Independent Review Committee for Crossover Participants	FAS	
2.4.4	Summary of Best Overall Response as Reported by Investigator for Crossover Participants	FAS	
2.4.5	Summary of Duration of Response as Determined by Independent Review Committee – Censoring Crossover Participants	FAS	
2.4.6	Summary of Duration of Response as Reported by Investigator – Censoring Crossover Participants	FAS	
2.4.7	Summary of Progression-Free Survival as Determined by Independent Review Committee – Censoring Crossover Participants	FAS	
2.4.8	Summary of Progression-Free Survival as Reported by Investigator – Censoring Crossover Participants	FAS	
Safety			
3.1.1	Summary of Exposure and Compliance	Safety	
3.1.2	Summary of Exposure and Average Daily Dose During Initial QD Dosing Period	Safety	
3.1.3	Summary of Exposure and Average Daily Dose During Maintenance Dosing Period	Safety	
3.2.1	Overall Summary of Treatment-Emergent Adverse Events	Safety	X
3.2.2	Summary of Treatment-Emergent Adverse Events by MedDRA System Organ Class and Preferred Term	Safety	X
3.2.3	Summary of Treatment-Emergent Adverse Events by MedDRA Preferred Term in Decreasing Order of Frequency	Safety	X
3.2.4	Summary of Treatment-Emergent Adverse Events by MedDRA System Organ Class, Preferred Term, and Maximum Severity	Safety	X
3.2.6	Summary of Grade 3 or Higher Treatment-Emergent Adverse Events by MedDRA System Organ Class and Preferred Term	Safety	X
3.2.7	Summary of Grade 3 or Higher Treatment-Emergent Adverse Events by Preferred Term in Decreasing Order of Frequency	Safety	X
3.2.8	Summary of Serious Treatment-Emergent Adverse Events by MedDRA System Organ Class and Preferred Term	Safety	X
3.2.9	Summary of Treatment-Emergent Serious Adverse Events by Preferred Term in Decreasing Order of Frequency	Safety	X
3.2.10	Summary of INCB050465 Treatment-Related Treatment-Emergent Adverse Events by MedDRA System Organ Class and Preferred Term	Safety	X
3.2.11	Summary of INCB050465 Treatment-Related Treatment-Emergent Adverse Events by MedDRA Preferred Term in Decreasing Order of Frequency	Safety	X
3.2.12	Summary of INCB050465 Treatment-Related Treatment-Emergent Adverse Events by MedDRA System Organ Class, Preferred Term, and Maximum Severity	Safety	X

Table No.	Title	Population	Standard
3.2.14	Summary of Grade 3 or Higher INCB050465 Treatment-Related Treatment-Emergent Adverse Events by MedDRA System Organ Class and Preferred Term	Safety	X
3.2.15	Summary of INCB050465 Treatment-Related Serious Treatment-Emergent Adverse Events by MedDRA System Organ Class and Preferred Term	Safety	X
3.2.16	Summary of Treatment-Emergent Adverse Events With a Fatal Outcome by MedDRA System Organ Class and Preferred Term	Safety	X
3.2.18	Summary of Treatment-Emergent Adverse Events Leading to INCB050465 Dose Reduction by MedDRA System Organ Class and Preferred Term	Safety	X
3.2.19	Summary of Treatment-Emergent Adverse Events Leading to INCB050465 Dose Interruption by MedDRA System Organ Class and Preferred Term	Safety	X
3.2.20	Summary of Treatment-Emergent Adverse Events Leading to Discontinuation of INCB050465 by MedDRA System Organ Class and Preferred Term	Safety	X
3.2.25	Summary of Treatment-Emergent Adverse Events by MedDRA Preferred Term and Maximum Severity in Decreasing Order of Frequency	Safety	
3.2.26	Summary of Selected Treatment-Emergent Adverse Events of Special Interest by Maximum Severity	Safety	
3.2.27	Summary of Time to Onset of Selected Treatment-Emergent Adverse Events of Special Interest	Safety	
3.2.28	Summary of Time to Onset of Selected Treatment-Emergent Adverse Events of Special Interest : Life-Table Method	Safety	
3.2.29	Summary of Longest Duration of Selected Treatment-Emergent Adverse Events of Special Interest	Safety	
3.3.1.1	Summary of Laboratory Values - Hematology	Safety	X
3.3.1.2	Summary of Laboratory Values - Chemistry	Safety	X
3.3.3.1	Shift Summary of Hematology Laboratory Values in CTC Grade - To the Worst Abnormal Value	Safety	X
3.3.3.2	Shift Summary of Chemistry Laboratory Values in CTC Grade - To the Worst Abnormal Value	Safety	X
3.3.3.4	Treatment-Emergent Worsening of Laboratory Abnormalities - Hematology	Safety	X
3.3.3.5	Treatment-Emergent Worsening of Laboratory Abnormalities - Chemistry	Safety	X
3.3.6	Time to Onset of Treatment-Emergent Worsening of Laboratory Events of Special Interest	Safety	
3.3.7	Time to Onset of Treatment-Emergent Worsening of Laboratory Events of Special Interest: Life-Table Method	Safety	
3.4.1	Summary of Systolic Blood Pressure	Safety	X
3.4.2	Summary of Diastolic Blood Pressure	Safety	X
3.4.3	Summary of Pulse	Safety	X
3.4.4	Summary of Respiratory Rate	Safety	X
3.4.5	Summary of Body Temperature	Safety	X
3.4.6	Summary of Weight	Safety	X
3.5.1	Summary of PR Interval (msec) From 12-Lead ECG	Safety	X
3.5.2	Summary of QRS Interval (msec) From 12-Lead ECG	Safety	X
3.5.3	Summary of QT Interval (msec) From 12-Lead ECG	Safety	X
3.5.4	Summary of QTcB Interval (msec) From 12-Lead ECG	Safety	X

Table No.	Title	Population	Standard
3.5.5	Summary of QTcF Interval (msec) From 12-Lead ECG	Safety	X
3.5.6	Summary of RR Interval (msec) From 12-Lead ECG	Safety	X
3.5.8	Summary of Outliers of QT, QTcB, and QTcF Interval Values From 12-Lead ECG	Safety	X
3.5.9	Summary of Clinically Significant ECG Abnormality	Safety	X

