5.4.3. Supportive Care Guidelines for Neutropenia and Thrombocytopenia

Neutropenia and thrombocytopenia appear to be PI3Kδ class-effect toxicities. Investigators should ensure that subjects understand the need to seek medical care when they have conditions that could become life-threatening in the presence of cytopenias (eg, neutropenic fever or bleeding with low platelets). Subjects should be instructed to report immediately any signs of infection, unexpected bleeding, or sudden, extremely painful headaches.

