9.4.2.2. Clinical Laboratory Tests

Laboratory data will be classified into Grades 1 through 4 using CTCAE v4.03 when applicable. The following summaries will be produced for the laboratory data:

- Descriptive statistics of the value and change from baseline at each assessment time will be provided.
- For laboratory parameters that have CTC grading, shift tables will be provided showing change in CTC grade from baseline to the worst grade postbaseline.
- For laboratory parameters where CTC grades are not defined, shift tables from baseline to the worst postbaseline value will be produced using the low/normal/high classifications based on laboratory reference ranges.

Categorical laboratory data will be tabulated by visit at baseline and postbaseline visits when necessary.

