### 3. STUDY DESIGN

This is a Phase 2, open-label study designed to evaluate the safety and efficacy of 2 INCB050465 treatment regimens in participants diagnosed with relapsed or refractory MZL (see [Figure 1](#)). The study was originally planned to enroll 2 Cohorts: Cohort 1, comprising 60 participants who had received prior ibrutinib, and Cohort 2, comprising 60 participants who had not received a prior BTK inhibitor. However, Cohort 1 was closed to further enrollment for feasibility reasons per Protocol Amendment (Version) 3. Participants enrolled in Cohort 1 and the first 60 participants in Cohort 2 will be further allocated to 1 of 2 study treatment regimens as follows:

[figure not shown]
- Treatment A: INCB050465 20 mg QD PO for 8 weeks followed by 20 mg QW PO.
  - Participants in Cohort 1 receiving Treatment A will be referred to as Cohort 1A.
  - Participants in Cohort 2 receiving Treatment A will be referred to as Cohort 2A.
- Treatment B: INCB050465 20 mg QD PO for 8 weeks followed by 2.5 mg QD PO.
  - Participants in Cohort 1 receiving Treatment B will be referred to as Cohort 1B.
  - Participants in Cohort 2 receiving Treatment B will be referred to as Cohort 2B.

An interim futility analysis is planned for Cohort 2 when 30 participants have been treated and evaluated for response or have permanently discontinued study treatment because of disease progression, withdrawal of consent, or death. Cohort 2 will be terminated for futility if  $\leq 10$  of the 30 participants responded (ie, CR or PR) based on assessments provided by an IRC; otherwise the study for Cohort 2 will continue.

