#### **9.3.2. Laboratory Value Summaries**

All test results and associated normal ranges from central laboratories will be reported in SI units. Any laboratory test results and associated normal ranges from local laboratories will be converted to SI units.

When there are multiple laboratory nonmissing values for a participant's particular test at a scheduled visit, central laboratory values have higher priority over local laboratory values. If a tie still exists, the laboratory value with the smallest laboratory sequence number will be used in by-visit summaries.

Numeric laboratory values will be summarized descriptively in SI units, and non-numeric test values will be tabulated when necessary. In addition, line graphs will be provided for ALT, AST, hemoglobin, platelet counts, leukocytes, neutrophils, and lymphocytes.

Shift tables will be presented showing change in CTCAE grade from baseline to worst grade postbaseline. Separate summaries for abnormally high and abnormally low laboratory values

will be provided when the laboratory parameter has both high and low grading criteria. The denominator for the percentage calculation will be the number of participants in the baseline category. The number of participants who experienced worsening of laboratory abnormalities will be summarized by maximum postbaseline severity.

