### **9.3.4. Worsening Laboratory Events of Special Interest**

Laboratory events of special interest are listed below.

- ALT increased
- AST increased
- Absolute neutrophil count decreased

The time to onset of a worsening laboratory event is defined as the interval between the date of first dose of study drug and the date of the first occurrence of CTC grade worse than baseline for the laboratory event. Participants who have not experienced a worsening laboratory event at the time of analysis will be right-censored at the last postbaseline study visit with nonmissing CTC grade of the laboratory event.

Time to onset of worsening Grade 3 or 4 laboratory events of special interest will be summarized using descriptive statistics and the life-table method as described in Section 9.2.2, and the Kaplan-Meier plot of time to onset of worsening Grade 3 or 4 absolute neutrophil count decreased will be provided. Laboratory events of special interest to be summarized may be adjusted based on emerging data.

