- Section 9.2.2 was updated to include details of analyses on time to onset of selected TEAEs of special interest. Summaries of longest duration of selected TEAEs of special interest were added to have a better understanding of the safety profile in terms of duration of class-effect AEs as well as AEs influenced by treatment regimens. "Grade 2 or higher" was changed to "Grade 3 or higher" for time to onset summary of rash. This change was made to be consistent with other PI3K inhibitors, which highlighted more severe cutaneous reactions graded as Grade 3 or higher in the labeling. "Herpes simplex virus infection" was changed to "herpes simplex" based on MedDRA coding dictionary

as a broader term. Exfoliative dermatitis was added to the list of TEAEs of special interest.

- Section 9.2.3 was updated to include summary of TEAEs by PT and maximum severity in decreasing order of frequency, summary of longest duration of selected TEAEs of special interest, and additional supporting summaries during the INCB050465 initial QD dosing period and the maintenance dosing period, which will provide supportive data of the safety profile of the maintenance dose. Summary of nonserious of TEAEs by SOC and PT was removed because it will not be used for the clinical study report but will be provided for result disclosure.
- Section 9.3.2 was modified to include ALT and AST in the line graphs as additional supportive analyses for laboratory events of special interest.
- Section 9.3.3 was added to identify potential Hy's law events to better monitor liver toxicity.
- Section 9.3.4 was updated to align with the analysis plan for adverse events of special interest. Summary of worsening of laboratory events of special interest was removed because this is covered by the summary of worsening of laboratory abnormalities.
- Section 9.5 was updated to change the high threshold of QTcF and QTcB interval from 460 to 450 milliseconds for purpose of analysis. This change is to comply with the categories outlined in FDA Guidance for Industry (E14 Clinical Evaluation of QT/QTc Interval Prolongation and Proarrhythmic Potential for Non-Antiarrhythmic Drugs) used to characterize outliers in QTc values.

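### The worst-grade laboratory tables are not split by dosing period, so they dilute differences between the two maintenance regimens

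*SAP*

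**What the plan says.** **Graded laboratory tables.** SAP 9.3.2 states: "Shift tables will be presented showing change in CTCAE grade from baseline to worst grade postbaseline". For the worsening tables it adds: "The number of participants who experienced worsening of laboratory abnormalities will be summarized by maximum postbaseline severity". Protocol 9.4.2.2 has the same rule for the shift tables: "shift tables will be provided showing change in CTC grade from baseline to the worst grade postbaseline". Appendix A lists two shift tables (3.3.3.1, titled "Shift Summary of Hematology Laboratory Values in CTC Grade - To the Worst Abnormal Value", and 3.3.3.2 for chemistry) and two worsening tables (3.3.3.4 and 3.3.3.5). None has a version by dosing period.

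**Regimens.** SAP section 3 gives "Treatment A: INCB050465 20 mg QD PO for 8 weeks followed by 20 mg QW PO". Treatment B has the same first 8 weeks and then 2.5 mg QD.

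**What is split by period.** Exposure (SAP 6.4) and treatment-emergent adverse events (SAP 9.2.3) are summarized separately for the initial QD and maintenance periods. The change log for SAP Amendment 1 records the addition of "additional supporting summaries during the INCB050465 initial QD dosing period and the maintenance dosing period" for adverse events, to support the description of safety on the maintenance dose.

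**Crossover.** Under SAP 5.2, a participant who switches after maintenance has begun goes into a separate Crossover group for safety summaries of the maintenance period. In every other summary that participant stays under the regimen first assigned.

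**Onset of laboratory events.** SAP 9.3.4 plans time to first Grade 3 or 4 worsening for ALT, AST and "Absolute neutrophil count decreased". Platelets are not on the list, although Protocol 5.4.3 says: "Neutropenia and thrombocytopenia appear to be PI3Kδ class-effect toxicities".

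**The concern.** The two regimens differ only after Week 8, and Protocol 1.4 and 1.5 explain the lower-intensity maintenance dosing as a way to reduce adverse events that lead to withdrawal. A table built on the worst grade since Day 1 mixes the shared 8 weeks with the period in which the regimens differ. A participant with a Grade 4 value at Week 4 is in the Grade 4 cell for good, whether the value recovers, persists or recurs on maintenance.

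Crossover adds to this. The Amendment 1 change log shows that 2.5 mg QD was selected, so late crossovers move from A to B. The laboratory tables have no maintenance period, so the Crossover group does not apply to them. A graded value first seen on 2.5 mg QD after a late switch would be counted under Treatment A.

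At stake is the descriptive safety profile by regimen for laboratory toxicities that the Protocol treats as expected. No inferential result is affected.

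**Working it through.** The plan states no figure on this point, so there is nothing to reproduce. The check has three parts.

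**1. How much does a whole-study window dilute a maintenance difference?**

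Let p0 be the risk of a given grade in the shared 8 weeks, and pX the risk on maintenance regimen X, independent of the early period.

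- Whole-study risk = 1 − (1 − p0)(1 − pX).
- Difference between regimens = (1 − p0)(p1 − p2).
- Share of affected participants already counted in the shared period = p0 / whole-study risk.

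The documents give none of these risks by period. Assume maintenance risks of 10% and 5%, that is, a 5.0-point difference and a ratio of 2.0, with p0 from 5% to 20%. For p0 = 10%: 1 − 0.90 × 0.90 = 19.0% and 1 − 0.90 × 0.95 = 14.5%.

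| Assumed p0 | 10% regimen shows | 5% regimen shows | Ratio | Difference (points) | Share already counted early |
|---|---|---|---|---|---|
| 5% | 14.5% | 9.8% (9.75%) | 1.49 | 4.75 | 34% to 51% |
| 10% | 19.0% | 14.5% | 1.31 | 4.5 | 53% to 69% |
| 20% | 28.0% | 24.0% | 1.17 | 4.0 | 71% to 83% |

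The ratio shrinks markedly and the absolute difference only slightly. If the same participants tend to have events in both periods, the attenuation is stronger than shown.

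**2. How large is the shared period?**

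Hematology is scheduled at Weeks 2, 4, 6 and 8 (4 samples), then every 4 weeks from Week 12 to Week 48 (10 samples). So 4 of 14 scheduled postbaseline samples through Week 48 fall in the shared period. Chemistry has 2 of 12 (Weeks 4 and 8, then 10 later). Against the expected treatment time of about 52 weeks, the shared period is 8/52, or about 15%.

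**3. What do the other planned outputs show about timing?**

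| Output | Covers | Does not cover |
|---|---|---|
| Adverse events by period, severity and regimen (SAP 9.2.3) | Laboratory values that qualify as adverse events, with Crossover separate | Graded values not reported as adverse events |
| By-visit summaries (SAP 5.1, 9.3.1) | Mean, median, minimum and maximum at each visit | Number of participants reaching each grade in each period |
| Listings 2.8.1 to 2.8.4 | Individual values | Any summary by regimen |
| Time to onset (SAP 9.3.4, Tables 3.3.6 and 3.3.7) | First Grade 3 or 4 ALT, AST and neutrophil events | Repeat events after an early first one; platelets; other parameters |

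Protocol Table 3 provides for restart after Grade 4 neutrophil or platelet counts and addresses recurrence, so repeat events are foreseen by the plan itself. SAP 9.2.2 and 9.3.4 do not state the life-table intervals, so a break at Day 56 is not assured.

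**The case against.** The strongest reply is that timing is visible elsewhere. Under Protocol 8.1.1 and 8.2, a laboratory abnormality is an adverse event if it is clinically meaningful or requires therapy or a change in study drug. Protocol Table 3 calls for interruption at the main Grade 3 and 4 cytopenias and transaminase rises, and Protocol 8.1.2 records each change in severity as a separate event. Much of the actionable Grade 3 or higher neutropenia and thrombocytopenia should therefore reach the period-split adverse event tables. This stands, though not completely: Protocol 5.4.1.1 allows transient laboratory values without symptoms to be exempt from the dose reduction guidelines, and lower-grade changes may never become adverse events.

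It is also true that worst-grade shift tables are specified in the Protocol and marked as standard in Appendix A, that SAP 3.2 plans no comparison between regimens, and that 2.5 mg QD had been selected by the time of SAP Amendment 1. Cells will be small. If about 30 participants are on the non-selected regimen (an assumption, since no allocation ratio is given), risks of 5% and 10% correspond to 1.5 and 3 participants. Split tables would describe such a difference, not establish it.

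A reader might infer more: that the shared 8 weeks dominate the tables, that regimen differences are hidden, or that the timing of thrombocytopenia is shown nowhere. The documents do not support this. They give no 8-week event rate. The Phase 1/2 study's Grade 3 or higher rates (anemia 7%, thrombocytopenia 10%, neutropenia 20%) cover a median of 122.5 days at several doses, with 31 of 72 subjects (27 + 4) on 30 or 45 mg. That study reported no liver function abnormality above Grade 1 on treatment, so early risks of 10% to 20% have no basis for transaminases. Thrombocytopenia reported as an adverse event is tabulated by period, and platelet counts are summarized by visit.

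**Conclusion.** The point holds as a limited gap in descriptive safety reporting. The four graded laboratory tables use a single whole-study window, unlike the adverse event tables, and keep late crossovers under their initial regimen. They dilute maintenance differences and cannot show by regimen whether graded abnormalities persist, recover or recur on maintenance. After allowing for the other outputs, three things are missing: a period-specific count of graded values not reported as adverse events, repeat events after an early first event, and laboratory-based onset for platelets.

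The size depends on assumed risks and on independence. A 2.0-fold maintenance contrast would show as 1.49- to 1.17-fold for early risks of 5% to 20%, while 95% to 80% of the absolute difference survives. With most scheduled samples falling in maintenance, dilution is the right description. This is a cheap improvement, and it does not touch the primary analysis.

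**What to change.** In SAP 9.3.2 and Appendix A:

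- Keep the overall versions of Tables 3.3.3.1, 3.3.3.2, 3.3.3.4 and 3.3.3.5, and repeat each for the initial QD and maintenance periods, using the periods of SAP 9.2.3.
- In the maintenance tables, include participants with at least one maintenance dose and a later laboratory value. Show late crossovers as a separate Crossover group, as SAP 5.2 provides for safety summaries of that period.
- Show the worst maintenance grade against two references: the Day 1 baseline, and the last value on or before the first maintenance dose. The second separates persistence from new worsening.
- Add platelet count decreased to the SAP 9.3.4 list, and so to Tables 3.3.6 and 3.3.7. That section already allows the list to change with emerging data.

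The cost is SAP wording and programming on data already collected. The downside is more descriptive tables with small cell counts.
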